# 4.6 Study Participants

# 4.6.1 Disposition of Participants

A clear accounting of the disposition of all participants who enter the study will be provided, from screening to study completion.

The following summaries will be provided:

- Number of subjects screened (including screen failures), number of subjects who were
  not randomized, and number of participants randomised and randomised not treated
  (including reason), number of participants started study treatment, as well as the
  number and percentage of subjects completed treatment and discontinued study
  treatment overall and by reason (including due to Coronavirus Disease 2019 [COVID19] pandemic), completed the study and withdrawn from the study by treatment group
  and overall.
- Number and percentage of subjects completed treatment and the study as well as the number and percentage of subjects discontinued and withdrawn from the study due to global/country situation. Number and percentage of participants recruited per region, country, and centre, by treatment group and overall, by population (SCR, FAS, PPS and SS).
- Number and percentage of Global/country situation (COVID 19) study disruption based on FAS.

A summary of stratification factors at randomization by treatment group and overall. The stratification factors are T2DM (Yes, No) and eGFR ( $\geq$ 20 to <30 mL/min/1.73 m^2; or  $\geq$ 30 to <45 mL/min/1.73 m^2; or  $\geq$ 45 mL/min/1.73 m^2) based on the latest eGFR assessment prior to the start of study treatment (eGFR assessment at Pre-randomization Visit 2). This summary will be provided for FAS.

By-participant listings of disposition details for discontinued participants, participants completing the study, participants affected by COVID-19 pandemic including the details will be provided. Discontinued participants are those that were not followed up to the last visit expected by the protocol, irrespective of reason and including participants who died prior to the last visit.

Additionally, a by-participant listing of the randomisation scheme and codes and the various batched of investigational products will be provided.

#### 4.6.2 Protocol Deviations

Important protocol deviations (IPD) are defined as those deviations from the protocol likely to have an impact on the perceived efficacy and/or safety of study treatments. The impact of important protocol deviations on the efficacy and/or safety results will be investigated by assessing the robustness of the study results and conclusions to the choice of analysis set, both including and excluding data potentially affected by important protocol deviations.

TP-GDO-WW-016-08 CONFIDENTIAL Project Document Version No. 3.0 Effective Date: 26 Nov 19 Project Document Effective Date: Date of last signature Related to: SOP-GDO-WW-019 Page 18 of 50

This estimation will be performed on a Blinded Data Review Meeting (BDRM) shortly before database lock/ unblinding. Results and population assignments will be summarized in a BDRM report which will be signed off by all relevant scientific experts.

Important protocol deviations and any action to be taken regarding the exclusion of subjects or affected data from specific analyses are defined in the project-specific Protocol Deviation Specification.

The IPD include the following:

- Inclusion/exclusion criteria deviations.
- Dosing deviations (eg, incorrect treatment received).
- Time window deviations for safety and/or PK assessments.
- Subjects receiving prohibited concomitant medications that are expected to influence the measurement of the primary endpoint.
- Subjects with at least one pandemic related important protocol deviation
- Other procedural and study conduct deviations recorded by the sites on a CSP deviation log.

The important protocol deviations will be summarised by treatment and overall on the FAS.

Important protocol deviations related to global/country situation (COVID-19) will be summarised separately by treatment and overall on the FAS. The following by-participant listings will be provided:

- Important protocol deviations
- Subjects affected by the COVID-19 pandemic

### 4.7 Demographic and Baseline Characteristics

Demographics and baseline characteristics will be summarized based on the FAS, by treatment group, and overall.

A summary of participants demographics at baseline will be provided for the following variables:

Demographics characteristics:

- Age (years)
- Age Group (years) [21 < 65 years, 65 < 85 years,  $\ge 85$  years]
- Sex
- Race
- Ethnicity
- Country

A summary of participants characteristics at baseline will be provided for the following groups of variables:

Baseline characteristics:

- Height (cm)
- Weight (kg)
- Weight Group (kg)  $[<40, \ge 40 < 75, \ge 75 < 90, \ge 90 < 120, \ge 120]$

- Body Mass Index (BMI) (kg/m²)
- BMI Group (kg/m²) [Underweight (<18.5), Normal weight ( $\ge18.5$  <25.0), Overweight ( $\ge25.0$  <30.0), Obese ( $\ge30.0$  to <35,  $\ge35$  to <40 and  $\ge40$ )]

Note: Body mass index less than 40 kg/m^2 is an inclusion criterion in the study.

#### Disease characteristics:

- T2DM status [yes/no]
- eGFR (mL/min/1.73m^2)
- eGFR Group [<30 mL/min/1.73 m², ≥30 to <45 mL/min/1.73 m², ≥45 mL/min/1.73 m²]
- NT-proBNP ≥300 pg/mL for patients with sinus rhythm and ≥600 pg/mL for patients with atrial fibrillation/flutter at screening or in medical history.
- HbA1C (%)
- LVEF (%)
- Clinical Chemistry parameters: Serum K+(mEq/L), Serum Na+ (mEq/L), serum Creatinine (mg/dL), SBP (mmHg) and DBP (mmHg)
- Haemoglobin (g/dl)
- UACR (mg/mmol)
- Nicotine use at screening (Current, Former, Never)
- Alcohol use at screening (Current, Former, Never)
- Number of patients in each of the 2nd and 3rd class of the NYHA functional classification

By-participant listings of demographics and participants characteristics at baseline will be provided for the randomised subjects.

### 4.7.1 Medical, Surgical History and Concomitant illnesses

Medical history and surgical history will be coded using Medical Dictionary for Regulatory Activities (MedDRA) version 23.0 or later.

Separate summaries will be provided for medical history and for surgical history. Each summary table will present the number and percentage of participants with any medical history conditions/surgical events by system organ class (SOC) and preferred term (PT) by treatment and overall for the FAS.

Medical and surgical history and concomitant illness will be listed by subject including treatment, description of the disease/procedure, MedDRA SOC, MedDRA PT, start date and stop date (or ongoing if applicable) based on the FAS.

Participants with multiple unique terms will be counted once per each unique PT and unique SOC. A participant can have one or more PTs reported under a given SOC. Each summary will be sorted by international order for System Organ Class and in alphabetical order for Preferred Term.

#### 4.8 Prior and Concomitant Medications

Medications (other than study drug) will be coded using the latest version of the World Health Organization Drug Dictionary (WHO-DD).

Medication start and stop dates will be compared to the date of first dose of study medication to allow medications to be classified as either Prior only, both Prior and Concomitant, or Concomitant only. Medications starting after the completion/withdrawal date will be listed but will not be classified or summarized.

Medications that start and stop prior to the enrolment will be classified as Prior only. If a medication starts before the date of enrolment and stops on or after the date of enrolment, then the medication will be classified as both Prior and Concomitant. Medications will be classified as Concomitant only if they have a start date on or after the date of enrolment

If medication start and/or stop dates are missing or partial, the dates will be compared as far as possible with the date of first dose of study medication. Medications will be assumed to be Concomitant only, unless there is clear evidence (through comparison of partial dates) to suggest that the medication started prior to the first dose of study medication. If there is clear evidence to suggest that the medication started prior to the first dose of study medication, the medication will be assumed to be both Prior and Concomitant, unless there is clear evidence to suggest that the medication stopped prior to the first dose of study medication. If there is clear evidence to suggest that the medication stopped prior to the first dose of study medication, the medication will be assumed to be Prior only.

All medications will be listed by patient for the enrolled set and will include the following information: reported name, anatomical therapeutic chemical (ATC), the route of administration, dosing frequency, total daily dose, study day of medication, duration of medication and therapy reason.

A summary of prior medications received and concomitant medications, by ATC level 3 code and PT by treatment and overall, on FAS will be reported.

Concomitant medications will be summarised by treatment group and overall, as:

- All concomitant medication taken during the study
- Disallowed concomitant medication taken during the study

The duration of medication will be calculated as:

$$Duration(days) = (end\ date - start\ date) + 1$$

The duration will be presented in days in the listing depending on the applicability to the emerging data. For medications with partial or completely missing start date and/or end date, the duration will not be calculated.

#### 4.9 Treatment Exposure/Compliance

Treatment compliance will be assessed separately for the 3 doses of AZD9977 (15, 50 and 150 mg) combined with dapagliflozin (10 mg) and for dapagliflozin (10 mg) alone. Compliance (as a percentage) will be calculated as follows:

$$Compliance (\%) = \frac{Number of capsules/tablets taken}{Number of capsules/tablets planned}$$

The number of capsules/tablets planned is equal to the treatment duration (days)\*number of planned capsules/tablets per day (3 capsules and 1 tablet daily). All tablets/capsules, including the placebo capsules, are to be counted. For subjects who withdraw prematurely from the study drug, compliance will be calculated up to the time of last dose.

TP-GDO-WW-016-08 CONFIDENTIAL Project Document Version No. 3.0 Effective Date: 26 Nov 19 Project Document Effective Date: Date of last signature Related to: SOP-GDO-WW-019 Page 21 of 50

The compliance will be summarized descriptively by treatment group and overall, on FAS. In addition, percent of compliance will be categorized into three groups, less than 80%, 80% to 120% and greater than 120%, and the categories will be summarized by treatment group and overall. In addition, listings for exposure and compliance of the investigational product will be also presented.

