4 STUDY DESIGN

4.1 Overall Design

This is a Phase 2b, multi-centre, randomised, double-blind, active-controlled parallel group, study to assess the efficacy, safety and tolerability of AZD9977 and dapagliflozin administered for 12 weeks in patients with HF and CKD (eGFR ≥ 20 and $\le 60 \text{ mL/min/1.73 m}^2$, with at least 20 % of patients with eGFR $\ge 20 \text{ to } < 30 \text{ mL/min/1.73 m}^2$ and a maximum of 35% of patients with eGFR $\ge 45 \text{ mL/min/1.73 m}^2$).

The study will be conducted at approximately 150 to 250 sites in approximately 20 countries including North America, Asia/Pacific, and European countries.

For each participant, the total duration of participation will be approximately 22 to 24 weeks, including a 1-week screening period, followed by up to 7-week run-in period followed by a 12-week treatment period (including 6 visits), the EOT visit, and a 4-week safety follow-up after last dose (including 1 visit). An optional pre-screening visit may be scheduled. Week and day for pre-screening visit will be at the discretion of the investigator.

After screening, eligible participants currently on treatment with a SGLT2i other than dapagliflozin should stop taking the SGLT2i and start on dapagliflozin 10 mg. Participants on dapagliflozin treatment will continue on treatment but the medication will be provided. Participants will then undergo a 4 to 5-week run-in period to ensure washout of forbidden medications and stable doses of allowed background medications.

For participants eligible after screening not on treatment with a SGLT2i, treatment with dapagliflozin 10 mg will be initiated. Participants will then undergo a 6 to 7-week run-in period to ensure washout of forbidden medications and stable doses of allowed background medications.

During the treatment period, participants will be randomly assigned in a 1:1:1:1 ratio to receive once daily administration of one of the 4 study treatments as described below. To ensure blinding, the study treatment will be administered in the form of 3 oral capsules and 1 oral tablet in the following combinations.

Study Treatment	Capsule 1	Capsule 2	Capsule 3	Tablet
AZD9977 15 mg + Dapagliflozin 10 mg	AZD9977 15 mg	Placebo	Placebo	Dapagliflozin 10 mg
AZD9977 50 mg + Dapagliflozin 10 mg	Placebo	AZD9977 50 mg	Placebo	Dapagliflozin 10 mg
AZD9977 150 mg + Dapagliflozin 10 mg	Placebo	AZD9977 50 mg	AZD9977 100 mg	Dapagliflozin 10 mg

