6.1 Study Intervention(s) Administered

6.1.1 Investigational Products

After screening, eligible participants currently on treatment with a SGLT2i other than dapagliflozin should stop taking the SGLT2i and start on dapagliflozin 10 mg once daily. Participants on dapagliflozin treatment will continue on treatment but the medication will be provided. Participants will then undergo a 4 to 5-week run-in period to ensure washout of forbidden medications and stable doses of allowed background medications.

For participants eligible after screening not on treatment with a SGLT2i, treatment with dapagliflozin 10 mg once daily will be initiated. Participants will then undergo a 6 to 7-week run-in period to ensure washout of forbidden medications and stable doses of allowed background medications.

Participants will be randomly assigned with a 1:1:1:1 ratio to receive once daily administration of one of the following study treatments:

- AZD9977 15 mg + dapagliflozin 10 mg
- AZD9977 50 mg + dapagliflozin 10 mg
- AZD9977 150 mg + dapagliflozin 10 mg
- Dapagliflozin 10 mg

To ensure blinding to treatment allocation and the AZD9977 dose, daily dosing will consist of 1 open label dapagliflozin 10 mg tablet and 3 AZD9977 capsules containing respectively AZD9977 150 mg or placebo, AZD9977 50 mg or placebo, and AZD9977 15 mg or placebo See Table 5 and Section 4.1.

	AZD9977				Dapagliflozin
Intervention Name	AZD9977 15 mg or placebo	AZD997 or placeb	U	AZD9977 100 mg or placebo	Dapagliflozin 10 mg
Туре	Drug	Drug	Drug Drug		Drug
Dose Formulation	Pellets in capsule (size 3)	Pellets in capsule (Pellets in capsule (size 0)	Film-coated tablet
Unit Dose Strength(s)	15 mg	50 mg		100 mg	10 mg
Dosage Level(s)	<pre>15 mg: 1 AZD9977 15 mg capsule + 1 placebo size 0 capsule + 1 placebo size 0 capsule 50 mg: 1 AZD9977 50 mg capsule + 1 placebo size 3 capsule + 1 placebo size 0 capsule 150 mg: 1 AZD9977 50 mg capsule +</pre>				10 mg tablet
	1 AZD9977 100 mg capsule + 1 placebo size 3 capsule				
Route of Administration	oral	oral	oral		oral
IMP and NIMP	IMP	IMP	IMP		IMP, NIMP ^a
Sourcing	AZD9977, dapagliflozin, and matching placebo treatments will be supplied centrally through AstraZeneca.				
Packaging and Labelling	For each strength, AZD9977 and matching placebo will be provided in bottles containing 32 capsules.Dapagliflozin will be supplied in HDPE bottles containing 35 tablets.				

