9.4.5.1 Adverse Events

Adverse events will be coded using the most recent version of the MedDRA that will have been released for execution at AstraZeneca or designee.

AEs will be presented for each treatment group by SOC and/or PT covering number and percentage of patients reporting at least 1 event and number of events where appropriate.

Only AEs occurring with an onset date, or worsening, on or after first dose of IMP and within 28 days after last dose of IMP will be presented in summary tables. Serious AEs occurring prior to start of IMP will be included in data listings.

An overview of AEs will present for each treatment group the number and percentage of patients with any AE, AEs with outcome of death, SAEs, and AEs leading to discontinuation of IMP, as well as AEs leading to IMP dose interruptions, and AEs leading to withdrawal from study as well as the number of individual occurrences in those categories.

Separate AE tables will be provided taken into consideration relationship as assessed by the investigator, maximum intensity, seriousness, death, and AEs leading to discontinuation of IMP as well as other action taken related to IMP, other significant AEs, and timing of events.

An additional table will present number and percentage of patients with most common AEs. Most common (eg, frequency of > 5%) will be defined in the SAP.

In accordance with the requirements of the FDA, a separate table will present non-serious AEs occurring in more than 5% of patients in any treatment group.

Key patient information will be presented for patients with AEs with outcome of death, SAEs, and AEs leading to discontinuation of IMP.

An AE listing for the SS will cover details for each individual AE; an AE listing for patients who were not exposed to IMP is presented separately.

Full details of AE analyses will be provided in the SAP.

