### 4.11.1 Extent of Exposure

The duration of exposure (days) will be summarized by treatment group separately for AZD9977 in combination with dapagliflozin and dapagliflozin alone. This will be derived as follows:

 $Duration\ of\ Exposure\ (Days) = Date\ of\ Last\ Dose\ - Date\ of\ First\ Dose\ +\ 1$ 

Treatment duration (days) will be summarized by treatment group for the SS, using descriptive statistics. A by-subject listing of drug administration data will be provided. Dates and times will be listed for each subject and treatment duration.

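### SAP 4.9 pools three capsules and one tablet into a single compliance figure, so a 15 mg or 50 mg participant can miss 67 of 84 active capsules and still be classed 80% to 120%

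*SAP*

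**What the plan says.** SAP 4.9 divides units taken by units planned. The denominator is treatment duration in days multiplied by the number of "planned capsules/tablets per day (3 capsules and 1 tablet daily"). It then adds: "All tablets/capsules, including the placebo capsules, are to be counted". The result is summarised by treatment group and sorted into three classes, "less than 80%, 80% to 120% and greater than 120" percent. The section opens by saying that compliance is assessed separately, but what it separates is the treatment groups, not the capsule strengths and not capsules from tablets. It gives no component-level figure; listings of exposure and compliance are added.

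Protocol 6.1.1, Table 5, sets out the daily units. The 15 mg arm takes "1 AZD9977 15 mg capsule + 1 placebo size 0 capsule + 1 placebo size 0 capsule" plus the dapagliflozin tablet. The 50 mg arm likewise has one active capsule and two placebos. The 150 mg arm has a 50 mg capsule, a 100 mg capsule and one placebo. Under Table 4 the control arm takes three placebo capsules. On packaging: "For each strength, AZD9977 and matching placebo will be provided in bottles containing 32 capsules".

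A second, smaller difference concerns adverse events. The AE overview in protocol 9.4.5.1 covers discontinuation "as well as AEs leading to IMP dose interruptions". The overview in SAP 4.11.2 has five rows, none for interruption, while SAP 4.14 reports no change to the planned analysis.

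**The concern.** The study is meant to establish a dose-response for AZD9977 on UACR. A reader will turn to the compliance table to judge whether the arms took the doses they were assigned. Under the pooled rule, three of the four daily units in the 15 mg and 50 mg arms are placebo or dapagliflozin, so the percentage mostly measures intake of something other than the drug being dose-ranged.

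Because each strength has its own bottle, skipping or losing one bottle while taking the others is a plausible failure. It would barely register in the pooled figure. A participant described as compliant could have taken an average AZD9977 dose below that of a lower arm.

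**Working it through.** **Inputs**
- Treatment length: protocol 4.1 gives a "12-week treatment period (including 6 visits"), that is 84 days. A full course is assumed.
- Planned units: 4 per day (SAP 4.9), so 84 × 4 = 336.
- Active capsules planned (protocol Tables 4 and 5): 84 in the 15 mg and 50 mg arms, 168 in the 150 mg arm.
- Planned mg in the 150 mg arm: 150 × 84 = 12,600.

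The plan states no figure of its own to reproduce. The 150 mg results use the 50 mg plus 100 mg composition in the tables. The sentence above Table 5 names a 150 mg capsule instead, and the two need reconciling.

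**Formula.** With *m* units missed, compliance = (336 − m)/336. It stays at or above 80% while m ≤ 0.20 × 336 = 67.2, so m = 67 is the limit. With *e* extra units, (336 + e)/336 ≤ 120% gives e ≤ 67.

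| Situation | Pooled compliance | Class |
|---|---|---|
| 15 or 50 mg arm, 67 of 84 active capsules missed (79.8%) | 269/336 = 80.1% | 80% to 120% |
| 15 or 50 mg arm, all 84 missed | 252/336 = 75.0% | below 80% |
| 150 mg arm, 67 of 168 active capsules missed (39.9%) | 269/336 = 80.1% | 80% to 120% |
| 150 mg arm, 84 of 168 missed | 252/336 = 75.0% | below 80% |
| One extra capsule on 67 of 84 days | 403/336 = 119.9% | 80% to 120% |
| One extra capsule every day | 420/336 = 125.0% | above 120% |

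**In mg at the limit**
- 15 mg arm: 15 × 17/84 = 3.0 mg/day.
- 50 mg arm: 50 × 17/84 = 10.1 mg/day, below the 15 mg arm's planned dose.
- 150 mg arm, if all 67 missed are 100 mg capsules: 6,700/12,600 = 53.2% of the mg dose lost.

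**Alternative reading: capsules only.** If the SAP's wording is taken to mean capsules and tablets counted separately, the capsule denominator is 84 × 3 = 252.
- The in-band limit is then 50 missed capsules: 202/252 = 80.2%.
- That is 50/84 = 59.5% of active capsules in the two lower arms and 50/168 = 29.8% in the 150 mg arm.
- Extra capsules on up to 50 days give 302/252 = 119.8%, in band; every day gives 336/252 = 133.3%, flagged.

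The problem shrinks but does not go away.

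**After reporting by strength.** The participant who missed 67 active capsules scores 17/84 = 20.2% on that capsule instead of 80.1%. Doubling one capsule on 67 days scores 151/84 = 179.8% instead of 119.9%.

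**The case against.** The case against a stronger reading is good, and most of it stands.

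- **A flat dose-response could not be told apart from poor intake.** A reader might infer this, but the documents do not support it. Predose AZD9977 samples are taken from all participants at Visits 5, 7 and 10 (protocol 1.3 and 8.5.1), and SAP 4.12.1 summarises, plots and lists them. Diaries and recorded regimen deviations (protocol 6.4) add to this. The dose/exposure-response plan that governs the secondary analysis was not available.
- **The primary result is affected.** Nothing in either document ties the bands to the primary model or to Per Protocol Set membership. They are descriptive.
- **Overdosing escapes detection.** Doubling the 100 mg capsule throughout gives 125% and is flagged; only doubling on 67 days or fewer is not. Supply may limit it further. If one 32-capsule bottle per strength is dispensed at each of Visits 3, 7, 8 and 9 (an assumption; bottles per visit are not stated), there are 128 − 84 = 44 spares, giving 380/336 = 113.1%, still in band. Protocol 8.4 also makes more than 150 mg of AZD9977 within 24 hours a reportable overdose, independently of the compliance table.
- **Most active capsules can be missed in every arm.** By count this holds only in the 15 mg and 50 mg arms.
- **The exposure formula hides interruptions.** SAP 4.11.1 states "The duration of exposure (days) will be summarized by treatment group separately" and uses last dose minus first dose plus 1, so interruption days count as exposed. But those days also stay in the compliance denominator, where they lower compliance, and dosing dates are listed. This is too weak to press.
- **The missing overview row loses the information.** Only in part: SAP 4.11.2 tabulates events by other action taken and includes drug interruption in its ordering of actions.

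None of this changes what the compliance percentage itself measures.

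**Conclusion.** The concern holds as a defect in descriptive reporting. In the 15 mg and 50 mg arms the 80% to 120% class is compatible with missing up to 80% of active capsules (60% on the capsules-only reading). In the 150 mg arm it is compatible with missing up to 40% of active capsules, or 53% of the mg dose (30% by count on the capsules-only reading). The table therefore cannot support a statement that participants took their assigned AZD9977 dose. It does not follow that the dose-response is uninterpretable or that the primary test is compromised.

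The figures assume an 84-day course and that all deviations fall on the capsule named. They are limits of the rule, not predictions: how many participants would behave this way cannot be known from the documents. That the Per Protocol Set is unaffected rests on the protocol and SAP. The Protocol Deviation Specification cited in SAP 4.6.2 was not available.

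The absent interruption row is a plain mismatch between SAP 4.11.2 and protocol 9.4.5.1 that SAP 4.14 does not declare.

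**What to change.** In SAP 4.9, report compliance and the three classes separately for capsules and for dapagliflozin tablets. Where the eCRF holds counts by bottle, report them for each capsule strength too, and after unblinding add AZD9977 mg taken over mg planned for the three AZD9977 arms. Splitting capsules from tablets alone still leaves the 50-of-84 limit shown above, so the strength-level figure is the one that closes the gap.

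In SAP 4.11.2, restore the overview row for adverse events leading to interruption of study drug.

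The cost is a few more table rows and one check. Protocol 6.4 requires records of tablets and of AZD9977/placebo capsules dispensed and taken, but does not say by bottle. SAP section 1 notes that the eCRF is to move to version 4.0, so this is the time to confirm or add bottle-level counts.
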